8. ANTI-TUMOR ACTIVITY ASSESSMENTS

Although the clinical benefit of SL-279252 has not yet been established, the intent of offering this IP is to provide a possible therapeutic benefit, and thus the participant will be carefully monitored for tumor response and symptom relief in addition to safety and tolerability.

For the purposes of this study, participants should be evaluated for response as outlined in the SOA. Confirmatory scans should be performed at least 4 weeks (>28 days), but no longer than 8 weeks after initial documentation of an objective response. All participants who receive at least 3 doses of SL-279252 and had the first disease assessment at the 8-week time point will be considered evaluable for response.

Assessments must be performed on a calendar schedule and should not be affected by dose interruptions or delays. Refer to the SOA (Section 6) for the schedule of disease assessments. More frequent disease assessments may be performed at the discretion of the investigator. For subjects whose disease may be followed by well-characterized tumor markers, disease assessments should include results of tumor marker assessments. If study treatment is withdrawn for reasons other than disease progression, radiographic disease assessments should continue as per the SOA until documented disease progression, the start of new anti-cancer therapy, withdrawal of consent or death. See Sections 8.3 for criteria for continuing treatment past disease progression.

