9.3 Populations for Analyses

For the analysis, the following populations are defined:

Population	Description
Enrolled	All subjects who sign the main study ICF.
Screen Failures	A subject who signs the informed consent but has not received any dose of SL-279252
All Treated	All subjects who receive at least one dose of SL-279252. Safety data will be evaluated based on this population.
DLT Evaluatable	All subjects in the All Treated population who receive at least 2 doses of SL-279252 for Schedule 1 or at least 3 doses for Schedule 2, complete the safety follow up through DLT evaluation period or experience any DLT during the DLT evaluation period. The DLT evaluation period is defined as the first 21 days or 28 days of treatment on Schedule 1 or Schedule 2, respectively. Evaluatable subjects will be used to guide dose escalation and to determine the MTD or MAD.
Evaluatable for Efficacy	A subject who received at least 3 doses of SL-279252 and had at least one post-baseline disease assessment or had progressed or died before the first post-baseline disease assessment. .
Pharmacokinetic	All subjects in the All Treated population who received at least one dose of SL-279252 and have at least one evaluable post-dose sample collected. The PK population will be used for PK analysis.
Pharmacodynamic	All subjects in the All Treated population for whom sufficient samples are available for the analysis. The pharmacodynamic population will be used for the pharmacodynamic data analysis.

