### 3.2 Dose Escalation

Two or more dosing schedules for SL-279252 may be evaluated:

- **Schedule 1:** administering SL-279252 on days 1, 8 and 15 of the first 28-day cycle and then every 2 weeks thereafter on days 1 and 15 of each 28- day cycle beginning with cycle 2.
- **Schedule 2:** weekly dosing of SL-279252 on days 1, 8, 15 and 22 of each 28-day cycle.

A less frequent dosing schedule (e.g., once every three weeks or once every four weeks) may be investigated if safety data from Schedule 1 indicates that this approach is most prudent.

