**Table 3. Analysis Populations**

Population	Description
Screened	All subjects who sign the main study informed consent form.
Screen Failures	A subject who signs the informed consent but has not received any dose of SL-279252.
All Treated	All subjects who receive at least one dose of SL-279252. Safety data will be evaluated based on this population.
DLT Evaluable	All subjects in the dose escalation cohorts and All Treated Population who receive at least 2 doses of SL-279252 for Schedule 1 and at least 3 doses for Schedule 2 during the DLT evaluation period, complete the safety follow up through DLT evaluation period or experience any DLT during the DLT evaluation period. The DLT evaluation period is defined as the first 21 days or 28 days of treatment on Schedule 1 or Schedule 2, respectively.
Efficacy Evaluable	All subjects in the All Treated Population who received at least 3 doses of SL-279252 and had at least one disease assessment or had progressed or died before the first post-baseline disease assessment.
Immunogenicity Population	All subjects in the All Treated Population who had at least one evaluable immunogenicity assessment.

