## 8. EFFICACY ANALYSES

The efficacy analysis will be based on the All Treated population and/or Efficacy Evaluable population, as appropriate. The efficacy endpoints include ORR, CBR, time to response (TTR), DOR, tumor size change from baseline for target lesions, PFS, and OS.

Response assessment will be based on the iRECIST for solid tumors and RECIL 2017 for lymphoma. Radiographic disease assessment must be performed at screening, and at the following intervals until a disease progression is confirmed: every 8 weeks through week 24, every 12 weeks

up to year 2 and then every 6 months up to conclusion of the study. Disease assessment window is +/- 1 week. Confirmatory assessments should be performed at least 4 weeks ( $\geq$  28 days) after the initial documentation of an objective response or an unconfirmed disease progression. Subjects who discontinue study treatment for reasons other than disease progression will be monitored for radiologic response until start of new anti-cancer therapy, disease progression, withdrawal of consent or death.

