## 8.5 Time to Response

TTR based on iRECIST is defined as the time from the first dose until the first documentation of a subsequently confirmed objective response (confirmed iCR or confirmed iPR). Only subjects who have achieved objective response will be evaluated for TTR.

TTR based on RECIST is defined as the time from the first dose until the first documentation of a subsequently confirmed objective response (confirmed CR or confirmed PR). Only subjects who have achieved objective response will be evaluated for TTR.

TTR based on RECIL 2017 is defined as the time from the first dose until the first documentation of an objective response (CR or PR). Only subjects who have achieved objective response will be evaluated for TTR.

If data warrants, the median and quartiles of TTR and their 95% CIs will be assessed using the Kaplan-Meier method and Brookmeyer and Crowley (1982) method, respectively, and TTR will be presented in a data listing.

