## 14. APPENDIX: LIST OF TABLES, FIGURES, AND LISTINGS

### 14.1 List of Tables

ICH Heading	Table Number	Table Description	Analysis Population
14.1		Demographics	
	14.1.1	Study Populations and Subject Disposition	All Screened
	14.1.2	Study Treatment Status	All Treated
	14.1.3	Protocol Deviations	All Treated
	14.1.4	Demographic and Baseline Characteristics	All Treated
	14.1.5	Study Cancer History	All Treated
	14.1.6	Prior Anti-Cancer Treatment	All Treated
14.2		Efficacy	
	14.2.1	Objective Response with Confirmation Based on iRECIST for Subjects with Solid Tumors	All Treated
	14.2.2	Objective Response with Confirmation Based on iRECIST for Subjects with Solid Tumors	Efficacy Evaluable
	14.2.3	Objective Response with Confirmation Based on RECIST 1.1 for Subjects with Solid Tumors	All Treated
	14.2.4	Objective Response with Confirmation Based on RECIST 1.1 for Subjects with Solid Tumors	Efficacy Evaluable
	14.2.5	Time to Response and Duration of Response Based on iRECIST for Subjects with Solid Tumors	Efficacy Evaluable
	14.2.6	Time to Response and Duration of Response Based on RECIST 1.1 for Subjects with Solid Tumors	Efficacy Evaluable
	14.2.7	Progression-Free Survival Based on iRECIST for Subjects with Solid Tumors	All Treated
	14.2.8	Progression-Free Survival Based on RECIST 1.1 for Subjects with Solid Tumors	All Treated
	14.2.9	Overall Survival for Subjects with Solid Tumors	All Treated
	14.2.10	Tumor Assessment at Baseline for Subjects with Solid Tumors	All Treated
14.3		Safety	
14.3.1		Study drug exposure/adverse event	
	14.3.1.1	Study Drug Exposure	All Treated
	14.3.1.2	Overall Summary of Treatment-Emergent Adverse Events	All Treated
	14.3.1.3	All Treatment-Emergent Adverse Events by System Organ Class, Preferred Term and Maximum Toxicity Grade	All Treated

ICH Heading	Table Number	Table Description	Analysis Population
	14.3.1.4	Drug-Related Treatment-Emergent Adverse Events by System Organ Class, Preferred Term and Maximum Toxicity	All Treated
	14.3.1.5	Immune Related Treatment-Emergent Adverse Events by Preferred Term and Maximum Toxicity Grade	All Treated
	14.3.1.6	All Treatment-Emergent Adverse Events by Preferred Term	All Treated
	14.3.1.7	Serious Treatment-Emergent Adverse Events by Preferred Term	All Treated
	14.3.1.8	Drug-Related Treatment-Emergent Adverse Events by Preferred Term	All Treated

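### The 3-dose rule for Efficacy Evaluable removes early toxicity stops, leaves early deaths undefined, and keeps any responder with fewer than 3 doses out of every TTR and DOR output

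*SAP*

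**What the plan says.** **Definition.** The Efficacy Evaluable row of SAP Table 3 covers treated subjects who "received at least 3 doses of SL-279252 and had at least one disease assessment or had progressed or died before the first post-baseline" assessment. Protocol 9.3 has the same structure: "A subject who received at least 3 doses of SL-279252 and had at least one post-baseline disease assessment", followed by the same alternative for early progression or death. Protocol Section 8 gives a different rule on who is evaluable for response: "All participants who receive at least 3 doses of SL-279252 and had the first disease assessment at the 8-week time point will be considered" to qualify. It makes no allowance for early progression or death.

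**Timing.** SAP 3.2 describes Schedule 1 as "administering SL-279252 on days 1, 8 and 15 of the first 28-day cycle", and Schedule 2 is weekly, so dose 3 is on Day 15 in both. A less frequent schedule is also allowed. The first scheduled scan is at week 8.

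**Which set is used.** SAP Section 8 opens with "The efficacy analysis will be based on the All Treated population and/or Efficacy Evaluable population, as appropriate". SAP 8.1.2, 8.2.2 and 8.4 then plan ORR and CBR in both sets without ranking them, and Protocol 9.4.2 names no set. PFS and OS use All Treated (SAP 8.9, 8.10).

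**TTR and DOR.** SAP 8.5 says "Only subjects who have achieved objective response will be evaluated for TTR", and SAP 8.6 has the matching rule for DOR. Neither sets a dose minimum. In the SAP 14.1 list, Table 14.2.5, "Time to Response and Duration of Response Based on iRECIST for Subjects with Solid Tumors", and its RECIST 1.1 counterpart, Table 14.2.6, are labelled Efficacy Evaluable. So are Figure 14.2.4 (DOR) and Listings 16.2.6.10 and 16.2.6.11.

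**Follow-up.** SAP Section 8 keeps scanning subjects who come off drug without progression, so a response after only 1 or 2 doses can be observed.

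**The concern.** A minimum-exposure rule applied after treatment starts selects on tolerability and early survival, both of which are related to outcome. Three things follow.

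- The Efficacy Evaluable denominator is not fully defined. Two programmers could treat a subject who died after dose 2 differently, and both would be following the text.
- With two ORR and CBR estimates of equal standing, the more favourable one can become the headline. Anti-tumor activity is one of the inputs to choosing the recommended Phase 2 dose.
- The responders behind TTR and DOR need not match the responders counted in All Treated ORR. The one left out would be a subject who responded after stopping early, which is informative for an immune agonist.

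**Working it through.** The documents attach no sample size or error rate to Efficacy Evaluable, so there is no stated figure to reproduce. The check is on the logic, followed by illustrations on assumed counts.

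**1. Day of dose 3.** Schedule 1: Days 1, 8, 15. Schedule 2: Days 1, 8, 15, 22. Every 3 weeks: Days 1, 22, 43. Every 4 weeks: Days 1, 29, 57, which is about the day of the first scan. The window for exclusion is therefore two weeks on the named schedules and wider on a less frequent one.

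**2. Who is in the set.** Reading A is (3 doses) and (assessed, or early progression or death). Reading B is (3 doses and assessed), or (early progression or death).

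| Subject | A | B | Protocol Section 8 |
|---|---|---|---|
| 1-2 doses, died or progressed before first scan | out | in | out |
| 1-2 doses, stopped for toxicity, no early progression or death, scanned or not | out | out | out |
| 1-2 doses, confirmed responder | out | out | out |
| 3 or more doses, died before first scan | in | in | out |
| 3 or more doses, responder who then stopped for toxicity | in | in | in, if scanned at week 8 |

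Rows 2 and 3 do not depend on the reading. A responder has a post-baseline scan and did not progress or die before it, so the second clause cannot bring that subject back. Row 1 depends entirely on the bracketing. Row 4 shows that Protocol Section 8 is a third version.

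**3. Effect on ORR.** Let p be the response rate in all treated subjects, f the share excluded and r the response rate among those excluded. The Efficacy Evaluable rate is (p - f × r)/(1 - f).

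- If r = 0, this is p/(1 - f). With an assumed 3 responders in an expansion cohort of 15 (SAP Section 4) and 2 non-responders excluded, f = 2/15 and 0.20/(13/15) = 0.231.
- If r = p, the rate is p, so there is no expected inflation.
- If r exceeds p, the rate falls.

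Exact (Clopper-Pearson) 95% intervals, the type of interval the SAP plans:

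| Excluded from 3/15 | Estimate | 95% CI |
|---|---|---|
| none (All Treated) | 3/15 = 20.0% | 4.3-48.1% |
| 1 non-responder | 3/14 = 21.4% | 4.7-50.8% |
| 2 non-responders | 3/13 = 23.1% | 5.0-53.8% |
| 3 non-responders | 3/12 = 25.0% | 5.5-57.2% |
| 1 responder | 2/14 = 14.3% | 1.8-42.8% |

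**4. Effect on TTR and DOR.** Expected responders lost = N × (share stopping for toxicity before dose 3) × (response rate among them). With N = 93, the larger total in SAP Section 4, and an assumed 5% stopping, response rates of 0%, 10% and 20% give 93 × 0.05 × 0 = 0, 93 × 0.05 × 0.10 = 0.47 and 93 × 0.05 × 0.20 = 0.93. The loss scales with the assumed 5%. Steps 3 and 4 are separate scenarios: the largest ORR inflation needs no response among the excluded, and the TTR/DOR loss needs some.

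**The case against.** Some stronger inferences are tempting, and the documents do not support them.

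- *Early deaths and progressions are dropped.* This holds only under reading A. The DLT Evaluable row of the same table has a similar form, and there the final clause evidently rescues subjects short of the dose minimum, which favours reading B. Protocol Section 8 points the other way. Documented progression before Day 15 would also be rare: the first scheduled scan is at week 8, and the SAP does not count clinical deterioration as progression.
- *Early failures vanish from ORR and CBR.* They do not. All Treated is committed for both endpoints, and Tables 14.2.1 and 14.2.3 report ORR in it. What is missing is a ranking.
- *All responders who stop for toxicity lose their TTR and DOR.* Only those with fewer than 3 doses do.
- *The plan's 15% acceptable rate of toxicity discontinuation measures the excluded share.* It is a monitoring rate for the expansion cohorts with no limit to the period before dose 3.

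It is also fair to say that these endpoints are secondary (ORR, CBR) or exploratory (TTR, DOR), that no efficacy hypothesis is tested, that TTR and DOR are summarised only if the data warrant it, and that an omitted responder would still appear in the All Treated response listings. A minimum-exposure set is a legitimate supportive analysis. One could add that SAP 8.5 and 8.6 restrict the analysis to responders rather than promise that every responder will appear.

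These arguments limit the size of the problem. They do not resolve the ambiguous sentence, the lack of a named main estimate, or the dose minimum that the TTR/DOR outputs impose and the text does not. SAP Section 12 does not mention or explain any of these.

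**Conclusion.** The point holds in this form. Under any reading, subjects who stop for toxicity after 1 or 2 doses without early progression or death leave Efficacy Evaluable, and a confirmed responder with fewer than 3 doses counts in All Treated ORR while having no TTR or DOR. Whether early deaths and progressions leave the set cannot be settled from the text.

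The numerical effect is modest: an illustrative shift of about 3 percentage points in a 15-subject cohort, well inside the interval, and on the 5% assumption about one responder or fewer missing from TTR and DOR across the study. All counts and rates behind these figures are assumed, and the direction of the ORR shift depends on how the excluded subjects respond. The change is worth making because responders will be few and the edits are nearly free.

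**What to change.** 1. In SAP 14, move Tables 14.2.5 and 14.2.6, Figure 14.2.4 and Listings 16.2.6.10 and 16.2.6.11 to all confirmed responders in All Treated (for RECIL, all responders, since SAP 8.3 requires no confirmation).
2. In SAP Table 3 and Protocol 9.3, bracket the definition so that subjects who progress, die or stop for drug-related toxicity before dose 3 are kept. Specify a post-baseline assessment in the SAP, as the protocol already does. Align the evaluability sentence in Protocol Section 8 with the result.
3. In SAP Section 8, name All Treated as the main population for ORR and CBR and Efficacy Evaluable as supportive, replacing the open choice in the opening sentence.

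The cost is SAP wording, relabelled output shells and a short protocol edit. No new data, extra subjects or change in treatment rules is involved. Efficacy Evaluable rates may become slightly less favourable, and that set moves closer to All Treated.

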## 7. STUDY POPULATION

Unless specified otherwise, all summary tables and data listings for this section will be based on the All Treated Population.

### 7.1 Subject Disposition

Summaries of subject disposition information will include the number of subjects in each analysis population, and the primary reason for end of study participation and treatment discontinuation. Subject disposition information will be presented in a data listing.

### 7.2 Protocol Deviations

Incidence of major protocol deviations, minor protocol deviations, and all deviations will be summarized by deviation categories. A listing will be provided with all protocol deviations. None of the deviations will lead to subjects being excluded from any analysis populations. Other select

categories of protocol deviations including but not limited to COVID-19 related deviations may be listed or summarized.

### **7.3 Demographic and Baseline Characteristics**

Demographic variables include age, sex, ethnicity, and race. Other baseline characteristics include weight and height.

Descriptive statistics will be presented for age, weight, and height. Frequency counts and percentages will be presented for age groups 18-<65 years, 65-<75 years and  $\geq 75$  years), gender, ethnicity and race. All demographic and baseline characteristics will be presented in a data listing.

### **7.4 Study Cancer History and Prior Cancer Therapy**

Study cancer history and prior cancer therapy will be summarized in tables and presented in data listings. For the calculation of time from initial diagnosis and time since progression on most recent regimen, if there are partial dates of initial diagnosis or partial dates of progression on most recent regimen, the missing day will be imputed as “01” and the missing month will be imputed as “January”.

### **7.5 General Medical History**

General medical history will be presented in a data listing.

### **7.6 Study Drug Exposure**

SL-279252 average dose received, number of doses received, duration of treatment, and dose compliance will be summarized.

Subject average dose is calculated as the cumulative dose (mg) that a subject received divided by the total number of doses received.

Duration of SL-279252 treatment will be summarized in weeks by continuous descriptive statistics and in the following categories:  $\leq 4$  weeks,  $> 4 - 8$  weeks,  $> 8 - 16$  weeks,  $> 16 - 24$  weeks,  $> 24 - 48$  weeks,  $> 48$  weeks. The duration of treatment is defined as:

- Minimum of (date of death plus 1 day, data cutoff date plus 1 day, and date of last dose + 14 days for bi-weekly dosing schedule or + 7 days for weekly dosing schedule) – date of first study drug administration Dose compliance is defined as the total mg of SL-279252 taken divided by the total mg of SL-279252 assigned based on study schedule, expressed as a percentage.

### **7.7 Prior and Concomitant Medications**

Verbatim terms on electronic case report forms (eCRFs) will be mapped to Anatomical Therapeutic Chemical (ATC) class and Generic Drug Names using the World Health Organization (WHO) Drug Dictionary Global B3 format, September 1, 2018 release.

Prior medications are defined as medications that end prior to the date of the first dose of study treatment. Concomitant medications are defined as medications taken on or after the date of the first dose of study drug. Any medications that started prior to the date of the first dose but continued beyond the date of first dose will be counted as concomitant medications.

If both the start and end dates are completely missing, the medication will be considered concomitant. For cases where start or end dates are partially recorded, the following imputation algorithms will be used for the purpose of determining prior or concomitant medications:

- Missing start day, but month and year present:

If year and month are same as first dosing year and month, assign the day of first dosing date to the partial date. Otherwise, assign 1st of the month to the partial date.

- Missing start day and month, but year present:

If year is same as first dosing year, assign the month and day of first dosing date to the partial date. Otherwise, assign January 1st to the partial date.

- Missing end day, but month and year present:

If year and month are same as end of study participation year and month, assign the day of end of study participation to the partial date. Otherwise, assign the last day of the month to the partial date.

- Missing end day and month, but year present:

If year is same as end of study participation year, assign the month and day of end of study participation date to the partial date. Otherwise, assign December 31st to the partial date.

If the study is ongoing (e.g. interim analysis) and the study end date is not available, the cut-off date will be used instead.

Prior and concomitant medications along with dose, route, start/end date, and indication for each medication will be presented in a data listing.

## 7.8 Concomitant Procedures

Concomitant procedures along with the procedure dates and indications will be presented in a data listing.

## 8. EFFICACY ANALYSES

The efficacy analysis will be based on the All Treated population and/or Efficacy Evaluable population, as appropriate. The efficacy endpoints include ORR, CBR, time to response (TTR), DOR, tumor size change from baseline for target lesions, PFS, and OS.

Response assessment will be based on the iRECIST for solid tumors and RECIL 2017 for lymphoma. Radiographic disease assessment must be performed at screening, and at the following intervals until a disease progression is confirmed: every 8 weeks through week 24, every 12 weeks

up to year 2 and then every 6 months up to conclusion of the study. Disease assessment window is +/- 1 week. Confirmatory assessments should be performed at least 4 weeks ( $\geq$  28 days) after the initial documentation of an objective response or an unconfirmed disease progression. Subjects who discontinue study treatment for reasons other than disease progression will be monitored for radiologic response until start of new anti-cancer therapy, disease progression, withdrawal of consent or death.

